6.4.1.1.7 Clinical Events of Special Interest

Clinical Events of Special Interest (CESI) are events relating to the detection of disease (SARS-CoV-2) activity relevant to the study vaccine. These events are analyzed separately from safety data; however, if the CESI demonstrates untoward signs or symptoms that, in the opinion of the Investigator, suggest the events are more likely related to study vaccine rather than to SARS-CoV-2, these signs/symptoms will be reported as AEs.

To be considered as a CESI of COVID-19 the following case definition adapted from the CBER Guidance: Development and Licensure of Vaccines to Prevent COVID-19 ([DHHS 2020](#)) must be met:

- The participant must have experienced at least 1 of the following systemic symptoms: fever ($\geq 38^{\circ}\text{C}$), chills, myalgia, headache, sore throat, congestion or runny nose, nausea or vomiting, diarrhea, fatigue, new olfactory and taste disorder(s), cough, shortness of breath, or difficulty breathing OR
- Clinical or radiographical evidence of pneumonia; AND
- The participant must have at least 1 test positive for SARS-CoV-2 by RT-PCR.

To be considered as a CESI of asymptomatic SARS-CoV-2 infection, a participant who demonstrates none of the COVID-19 symptoms described above but who tests positive for SARS-CoV-2 on PCR test or anti-nucleocapsid antibody test (if nucleocapsid antibody negative prior to entry into the study) will be counted.

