8.2. Analysis of Immunogenicity Primary and Secondary Endpoints

8.2.1. Analysis of primary and secondary immunogenicity endpoints

Total NAbS and BAbS titers will be summarized using descriptive statistics (number of subjects (n), median, minimum and maximum) by each time point in priming vaccination period (Baseline, Days 14, 28, 42, 56, 208) and booster vaccination period (Day 208, 236, Early Termination). Summaries of priming vaccination and booster vaccination periods based on their corresponding mITT and PP analysis sets will be presented separately using the applicable treatment groups (Table 4-1). For the analysis of booster mITT analysis set, summary tables with active boosters pooled (as presented in Table 4-1; e.g., A1, A2, B1, B2, etc.) will also be presented.

The following statistics will be provided in the summary tables and/or figures:

- Geometric mean titer (GMT) with corresponding 95% CI will be provided at each time point. The 95% CIs will be calculated based on the t-distribution of the log-transformed values then back transformed to the original scale for presentation. GMT level and corresponding 95% CI will be plotted at each timepoint in priming vaccination period for mITT analysis set. Plots of the reverse cumulative distribution curves also will be provided by treatment group and visit in priming vaccination period for mITT analysis set.
- Geometric mean fold rise (GMFR) with corresponding 95% CI will be provided at each post-baseline timepoint over baseline. The 95% CIs will be calculated based on the t-distribution of the log-transformed values then back transformed to the original scale for

presentation. GMFR and corresponding 95% CI will be plotted at each timepoint in priming vaccination period for mITT analysis set.

- The number and percentage of subjects with fold-rise ≥ 2 and fold-rise ≥ 4 from baseline (Seroconversion) at each post baseline time points will be tabulated with the 2-sided 95% CI using the Clopper Pearson method at each post-baseline timepoint.
- Seropositivity at a participant level is defined as any detectable antibody level above the lower limit of quantification (LLOQ) for the specific assay and antibody measured at timepoints after baseline. Seropositivity rates will be provided with 2-sided 95% CI using the Clopper-Pearson method at each post-baseline time point.

The definition of seroconversion/seropositivity may depend on assay-specific performance characteristics. The conventions are as follows:

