8.3.2. CMI Analysis

CMI responses will be evaluated for CMI subset using parametric flow cytometry for quantification and phenotyping and cytokine staining for TNF- α , IL-2, IFN- γ , IL-4, and IL-13. Blood sampling will be performed at Days 0, 14, 28, 42, 56, 208, 215, 236, and Early Termination in participants enrolled at centers identified with capabilities for isolation of peripheral blood mononuclear cells (PBMCs). CMI testing will not be performed on participants re-enrolling at Day 98-198 (i.e., placebo participants who re-enter the study to receive ARCT-021 priming vaccinations).

Descriptive statistics (N, mean, SD, min, Q1, median, Q3, max) will be provided for each visit including change from baseline at each timepoint, where CMI results are available for the priming vaccination period (mITT and PP analysis CMI subsets) and booster vaccination period (Booster mITT CMI subset). When summarizing the Early Termination visit, only include observations within the booster vaccination period post day 236. The following CMI responses will be summarized:

- CD4+ T-cell responses background subtracted (combined pools): IFN- γ , TNF- α , IL-2, IFN- γ + TNF- α +, IFN- γ + TNF- α + IL-2+
- CD8+ T-cell responses background subtracted (combined pools): IFN- γ , TNF- α , IL-2, IFN- γ + TNF- α +, IFN- γ + TNF- α + IL-2+

- Th1/Th2 CD4+ T-cell responses background subtracted (combined pools): IFN- γ , IL-4, IL-4+ IL-13+, IFN- γ + / IL4+ IL13+

Box plots will be provided for the following for priming vaccination period (mITT CMI subset): CD4+/CD8+ IFN γ , IL4+IL13+, IFN γ +/IL4+IL13+, Th1/Th2.

Analyses will be performed overall and by age group (younger adults (≥ 18 - < 56 years), older adults (≥ 56 years)) for priming vaccination period (mITT CMI subset).

Summary tables and figures will exclude any data points collected at or after the first occurrence of the following intercurrent events: death, missed second ARCT-021 (if applicable) dose, use of immune-modifying drugs, and study infection. Summary tables and figures will exclude all data from subjects with early (before Day 7), active or prior SARS-CoV-2 infection at first vaccination.

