^g Immunogenicity samples will include anti-SARS-CoV-2 neutralizing and binding antibodies. On days when study vaccines are administered, blood must be drawn prior to vaccine administration. On unscheduled visits that are performed for assessment of non-COVID-19-related AEs, a blood sample for immunogenicity is not required.

^h At each timepoint blood will be drawn in the participants assigned to the CMI subset. On days when study vaccines are administered, blood must be drawn prior to vaccine administration. Participants assigned to the CMI subset and who re-enroll into the study will not undergo blood sampling for CMI after re-enrollment.

ⁱ Nasal swabs and nasal turbinate swabs may replace saliva testing with alternate means of confirmatory testing of SARS-CoV-2. Participants will receive Home Test Kits if the participant reports possible COVID-19 symptoms or risk of exposure to SARS-CoV-2.

^j Study vaccine will be administered by intramuscular injection into the deltoid muscle of the non-dominant arm. Study vaccine administration will not be performed at these visits if the participant has not met reasons for study vaccine withdrawal.

^k Vaccinated participants will be observed at the site for at least 30 minutes following vaccine administration or until clinically stable.

^l Review of AEs will include surveillance for solicited and unsolicited AEs, SAEs, MAAEs, NOCDs, AEs leading to next vaccine delayed or vaccine will not be re-dosed; data will be gathered by Diary and telephone contacts.

^m At telephone contacts performed from Day 98 through Day 198, participants will be asked if they are interested in re-enrolling into the study to receive ARCT-021 vaccine. Participants eligible to re-enroll to receive ARCT-021 vaccine (placebo group only), will complete the Early Termination visit.

Schedule of Events: Booster Vaccinations

Visit Type (Study Day)	Booster Administration	Booster Follow-up 1	Study Calls	Booster Follow-up 2	Study Calls	Booster Follow-up 3 ^l	Study Calls	Unscheduled Visit	Early Termination	Final Visit
	Clinic	Clinic ^a	TC	Clinic ^a	TC	Clinic ^a	TC	Clinic ^a	Clinic ^a	Clinic ^a
Study Day	208	215	222, 229	236	264, 292, 320, 348, 376	388	416, 444, 472 500, 528, 556	n/a	n/a	570
Procedure/Visit Window (in days)	+60	0	±3	±3	±3	±3	±3	n/a	n/a	+7
Physical examination ^b	X	X		X		X		X	X	X
Vital signs, pulse oximetry, and body temperature ^c	X	X		X		X		X	X	X
Pregnancy test ^d	X									
Blood sampling for safety ^e	X	X								

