13.5. Appendix 3: Estimands and Intercurrent Events

Possible intercurrent events are presented in the table below.

Table 13-3 **Intercurrent Event Types**

Label	Intercurrent Event Type
IcEv1 (Death)	Death due to any cause (including pneumonia) other than COVID-19.
IcEv2 (Missed dose)	Does not receive the second vaccination at Day 28 where second vaccination assigned was ARCT-021 or does not receive booster vaccination at Day 208 where booster vaccination assigned was active ARCT booster. It is not necessary to exclude placebo missed second doses as there is no impact.
IcEv3 (Immune-modifying)	Use of immune-modifying drugs or non-study vaccines which interfere with immunogenicity. Immune-modifying drugs will be determined from a medical review of medications taken during the study.
IcEv4 (Early infection)	
Priming vaccination period: Antigens or antibodies indicating exposure to SARS-CoV-2 prior to vaccination or early infection before Day 7. (This IcEv is particularly relevant to assessing immunogenicity.) Early infection is defined as follows:
 
 ○ Positive PCR saliva test at baseline OR ○ Positive PCR test at any time up to 7 days post-baseline OR ○ Positive SARS-CoV-2 baseline serostatus 
Booster vaccination period: Antigens or antibodies indicating exposure to SARS-CoV-2 prior to vaccination or early infection before Day 7 post booster vaccination. (This IcEv is particularly relevant to assessing immunogenicity.) Early infection for different boosters is defined as follows:
 
 ○ Positive PCR saliva test on Day 208 OR the booster vaccination OR ○ Positive PCR test at any time up to 7 days post-booster vaccination
IcEv5 (Study infection)	Develops COVID-19 or asymptomatic SARS-CoV-2 infection on or after Day 7. (This IcEv is particularly relevant to immunogenicity and CESI events.). Study infection is defined as COVID-19 infection recorded on the adverse event CRF page with start date on or after Day 7. The following AE preferred terms will be considered: Asymptomatic COVID-19, COVID-19, Suspected COVID-19. Positive MSD nucleocapsid antibody value of 5000 AU/mL or higher at any point after baseline (with start date on or after Day 7) will also be considered as on-study infection.

Attributes for the primary safety estimands with strategies for IcEvs are presented in Table 13-4 below.

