Estimand Label	Estimand 2 (Geometric Mean Titers/Concentrations)
Estimand Description	
The GMT of NAbs (primary) and BAbs (secondary) against SARS-CoV-2 up to Early Termination after first vaccination with ARCT-021 of each group (5.0, 7.5 µg, or placebo) and with/without booster dose in healthy adults.
 
Interest will lie in comparing the GMT of each dosing regimen to placebo based on the Geometric Mean Ratio (GMR).
 
The hypothetical strategy is used to estimate antibody levels had all scheduled vaccinations been received, and without subsequent SARS-CoV-2 infection or influence from immune-modifying drugs or non-study vaccines. The principal stratum strategy excludes those with active or early SARS-CoV-2 infection within 7 days after the first study vaccine administration.

Analysis Population	Vaccinated healthy adults (as defined by eligibility criteria) without active or early SARS-CoV-2 infection (infection within 7 days after the first vaccination).
Endpoint	Total NAbs (primary) and BAbs (secondary) specific for the SARS-CoV-2 measured pre- and post-priming vaccine administration (on Day 0, 14, 28, 42, 56, and 208) and following booster vaccine administration (Day 236, Early Termination).
Treatment Conditions	Placebo or 5.0 µg or 7.5 µg ARCT-021 administered on Day 0, Day 28; placebo, ARCT-021, ARCT-154, or ARCT-165 administered on Day 208.
Population-Level Summary	The GMT and GMR of comparisons of interest at each time point. GMR will compare responses in placebo-, ARCT-021-, ARCT-154-, and ARCT-165-vaccinated groups at relevant timepoints. For additional considerations on population-level summary see the SAP.
Intercurrent Event Strategy	
IcEv1 (Death)	Hypothetical strategy
IcEv2 (Missed dose)	Hypothetical strategy
IcEv3 (Immune-modifying)	Hypothetical strategy
IcEv4 (Early infection)	Principal stratum strategy (based on study phase)
IcEv5 (Study infection)	Hypothetical strategy
Rationale for Strategies	Hypothetical strategy is used to understand antibody levels achieved through receiving scheduled vaccination, without subsequent SARS-CoV-2 infection and without any influence from immune-modifying drugs or non-study vaccines. In estimation, the hypothetical uses a statistical model on the mITT (excluding data points following intercurrent events and not complete removal of all data for the participant).

Estimand Label	Estimand 3 (Rise/Seroconversion)

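### The SAP does not date a serology-detected infection, and read literally it keeps the first N-positive sample's titres in the antibody estimands

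*SAP*

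**What the plan says.** SAP Table 13-5 gives on-study infection the same strategy in Estimands 2 and 3: "IcEv5 (Study infection) Hypothetical strategy". The target is the antibody response that vaccination would produce in the absence of infection. The rationale rows carry this out by "excluding data points following intercurrent events and not complete removal of all data for the participant", and Protocol Table 7-2 uses the same words.

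SAP Table 13-3 gives two routes into IcEv5. One is the adverse-event page: "Study infection is defined as COVID-19 infection recorded on the adverse event CRF page with start date on or after Day 7". The other is serology: "Positive MSD nucleocapsid antibody value of 5000 AU/mL or higher at any point after baseline (with start date on or after Day 7". An adverse event has a recorded start date. An antibody value has only a collection date, and the SAP does not say whether that is the start date it means.

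No other section settles this for the antibody analyses. SAP 8.2.1 and 8.2.2 contain no infection rule, and the censoring column of Table 13-6 deals only with values below LOQ or LOD. For cell-mediated immunity, SAP 8.3.2 is explicit and different: "Summary tables and figures will exclude any data points collected at or after the first occurrence of the following intercurrent events", with study infection on its list. Nothing extends that sentence to the antibody tables.

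**The concern.** The N result and the titres of interest come from the same visit. SAP Appendix 1 states: "Immunogenicity samples will include anti-SARS-CoV-2 neutralizing and binding antibodies". N is one of the three antigens in the MSD multiplex assay (SAP 8.1.2). The vaccines encode spike only (Protocol 5.3), and SAP 8.2.1 ties the 5000 AU/mL threshold to infection or viral exposure. The first N-positive sample is therefore already a post-infection sample. If the event is dated to that draw and only later draws are removed, the infection response stays in the analysis of that visit.

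In placebo, where titres would otherwise sit near half the LLOQ, a retained infection raises the GMT and the seroconversion rate, and so shrinks the ratio and the rate differences. In the vaccine groups it makes Day 208 persistence and the Day 236 post-booster summaries look better than vaccination alone. Two programmers working from the same text could produce different values for a primary endpoint.

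**Working it through.** **1. The plan's own figure.** The only stated figure for the antibody comparison is power above 99% for a 2-fold difference at 75:75 with SD 1.2 on the natural log scale (Protocol 7.3, SAP 4.2). With d = ln 2 = 0.693 and a two-sided 5% level, I get 94.3% (94.0% by noncentral t). Power above 99% appears only at 150:150 (99.9%) or 75:225 (99.1%). That is a separate matter; 94.3% serves here only as the base for the cost of exclusion.

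**2. Where the exposure lies.** SAP 8.2.1 lists the "priming vaccination period (Baseline, Days 14, 28, 42, 56, 208". The gaps between successive draws are 14 days up to Day 56, then 208 − 56 = 152 days. With the +60-day booster window the last gap can nominally reach 212 days. An infection in that interval that leaves only a serological trace is first seen at Day 208.

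**3. Effect of keeping the revealing sample.** Let a share q of the placebo group have a retained sample at F times its uninfected level. On the log scale the placebo mean rises by q ln F, so the placebo GMT is multiplied by F^q and the GMR by F^(−q). Neither q nor F is in the documents; both are assumed. Vaccine-arm contamination is set to zero at first.

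| q | F | Placebo GMT × | GMR × | True 2-fold GMR estimated as |
|---|---|---|---|---|
| 2% | 4 | 1.028 | 0.973 | 1.945 |
| 2% | 30 | 1.070 | 0.934 | 1.868 |
| 5% | 10 | 1.122 | 0.891 | 1.783 |
| 10% | 4 | 1.149 | 0.871 | 1.741 |
| 10% | 30 | 1.405 | 0.712 | 1.423 |

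A second set of assumptions starts from the assay. Half the neutralizing LLOQ is 7.843/2 = 3.92 IU/mL (SAP 8.2.1). Take infected titres of 50 to 200 IU/mL, so F = 50/3.92 = 12.8 to 200/3.92 = 51, and q from 2.5% to 10%:

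- low end: 12.8^0.025 = 1.066, GMR × 0.938
- middle: (100/3.92)^0.05 = 1.18, GMR × 0.85
- high end: 51^0.10 = 1.482, GMR × 0.675

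Together the two sets span placebo GMT inflation of about 3% to 48%. With F of at least 4, placebo 4-fold seroconversion rises by up to q, that is, by up to 2 to 10 percentage points.

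**4. Allowing for the vaccine arm.** If a vaccine group also keeps a share q_v at F_v times its own level, the GMR factor is F_v^(q_v)/F^q. For example, q = q_v = 5%, F = 10 and F_v = 2 give 1.035 × 0.891 = 0.92 instead of 0.89. The zero-contamination figures are thus the larger attenuation.

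**5. Cost of excluding the sample.** If each group falls from 75 to 75(1 − q), power goes from 94.3% to 93.8%, 93.2% and 91.9% for q = 2%, 5% and 10%. Protocol 7.2 plans no hypothesis test, so read this as a small loss of precision.

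**The case against.** A reader might infer that the SAP dates a serology-detected infection to the sample that reveals it, so that the no-infection estimand is certainly not what is estimated. The documents do not go that far. The start date of a laboratory value is undefined. Table 13-3 describes the event as developing infection, which precedes the positive sample, so a programmer could treat that sample as already following the event. Draw-dating is the natural reading, but it is an inference.

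Other routes also catch cases earlier. Saliva PCR is taken at every scheduled clinic visit after screening. Unscheduled COVID-19 visits and Early Termination visits include antibody sampling. Calls on Days 70 to 198 ask about symptoms and exposure. Protocol 6.4.1.1.7 counts as asymptomatic infection a symptom-free participant who "tests positive for SARS-CoV-2 on PCR test or anti-nucleocapsid antibody test", and SAP 9.1 has such cases entered as adverse events. This narrows the problem but does not close it. Table 13-3 lists serology as an additional route, Protocol 6.1 says central-laboratory N results are not diagnostic tests, and no rule says what start date a site enters for a laboratory-only case. The booster-period definition of early infection uses PCR alone, so it does not catch a PCR-negative, N-positive Day 208 sample.

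It is also tempting to claim a biased booster GMR at Day 236. None is planned: the ANCOVA covers the priming period only (SAP 8.2.2.1), and booster immunogenicity is exploratory. The ratios and rate differences are supportive, the Phase 3 dose had already been chosen (Protocol 7.8), and SAP Section 1 warns that interpretation beyond Day 56 may be limited. These facts lower the stakes. They do not remove the primary GMT and seroconversion summaries, which cover all time points.

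**Conclusion.** The point holds as a gap with a literal reading that goes the wrong way. The SAP does not define the onset of an N-detected infection. With the event dated to the draw, the revealing sample stays in that visit's antibody summaries and ANCOVA, against both the stated hypothetical strategy and the rule in SAP 8.3.2. The direction is clear for placebo: GMT and seroconversion go up, GMR and rate differences go down. The size cannot be derived from the documents. The 3% to 48% range rests on assumed infection shares and titre rises, with uninfected placebo near half the LLOQ for the upper set; the top figure combines both upper-end assumptions. Exposure is greatest at Day 208 and is confined to infections that no other route dates earlier. The change should be made because it is cheap and fixes the handling of a primary endpoint.

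**What to change.** For infection (IcEv5) only, amend the Estimand 2 and 3 rows of SAP Table 13-5, and add the same rule to SAP 8.2.1 and the censoring column of Table 13-6, which now have none:

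*Data points collected at or after the earlier of the AE start date or the first sample with N ≥5000 AU/mL are excluded from NAb, spike, RBD and sVNT summaries and models; N-antibody tables retain them.*

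Do not apply *at or after* to missed doses. Blood on vaccination days is drawn before dosing (SAP Appendix 1), so the Day 28 or Day 208 pre-dose value is unaffected by a dose missed that day. Copying the 8.3.2 sentence whole would risk discarding those values, because its list includes a missed second dose.

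The cost is one programming condition and a few data points per visit. The SAP states that it prevails over the protocol where methods differ, so an entry in SAP Section 11 is enough to record the change.

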13.6. Overview of Statistical Methods: Estimation of Estimands and Supportive Analyses

A summary of the statistical methods and sensitivity analyses is presented in [Table 13-6](#). Placebo participants will be pooled across dose groups summaries.

Table 13-6 **Summary of Statistical Methods and Supportive Analyses**

Estimand Label	Estimand Description	Analysis Set	Imputation/ Data/ Censoring Rules	Main Estimation	Supportive Analysis
				Analysis Model/Method	
Estimand 2	
The GMT of total NAbs (primary) and GMC of BAbs (secondary) titers against SARS-CoV-2 from Day 14 up to Early Termination after initial priming vaccination with ARCT-021 and booster vaccinations (ARCT-021, ARCT-154, and ARCT-165) (exploratory) of each dose in healthy adults. Interest will lie in comparing the GMC of each dosing regimen to placebo (GMR).
 
The hypothetical strategy is used to estimate antibody levels had both scheduled vaccinations been received, and without any influence from immune-modifying drugs or non-study vaccines, or subsequent SARS-CoV-2 infection.
	mITT	
Values below the limit of quantification (LOQ) or limit of detection (LOD) will be replaced by LOQ/2 and LOD/2, respectively.
	
Total NAbs and BAbs levels will be summarized with descriptive statistics, including boxplots (on log scale versus time) by time point: Days 14, 28, 42, 56, 208, 236, Early Termination. GMTs with corresponding 95% CI will be provided at each time point. The 95% CIs will be calculated based on the t-distribution of the log-transformed values then back transformed to the original scale. GMFRs with corresponding 95% CI will be provided at each post-baseline timepoint over baseline. The 95% CIs will be calculated based on the t-distribution of the log-transformed values then back transformed to the original scale.
	
Supportive: For the priming vaccination period ANCOVA will be fitted to the natural log transformed antibody titers and antibody concentrations measured against SARS-CoV-2 with terms for treatment group, age group and natural log baseline titer by each post-vaccination immunogenicity visit. The geometric least squares mean (GLSM) and corresponding 2-sided 95% CI for each treatment group will be provided by visit. Geometric mean ratio (GMR), estimated by the ratio of GLSM, and the corresponding 95% CI will be provided to assess the difference between ARCT-021 vs. placebo groups at each visit.
 
Descriptive statistics, GMT/GMFRs based on t-distribution will be presented by the following analysis subgroups: age group, gender and country. ANCOVA models will be presented by gender and country.

Table 13-6 **Summary of Statistical Methods and Supportive Analyses**

Estimand Label	Estimand Description	Analysis Set	Main Estimation		Supportive Analysis
			Imputation/ Data/ Censoring Rules	Analysis Model/Method	
Estimand 3	
Percentage of participants with at least 2- and 4-fold increase in antibody responses from baseline (seroconversion) in NAbs (primary) and BAbs (secondary) at each time point from Day 14 to Early Termination after initial priming vaccination with ARCT-021 (for each dose and placebo), and booster vaccinations (ARCT-021, ARCT-154, and ARCT-165) (exploratory) in healthy adults.
 
Same hypothetical/principal stratum strategies and vaccine groups as for Estimand 2.
	mITT	
Titer values below the LOQ or LOD will be replaced by LOQ/2 and LOD/2, respectively, prior to calculation of fold changes and seroconversion.
	
The number and percentage of participants with \geq 2- and 4-fold increase from baseline will be provided with 2-sided 95% CI using the Clopper-Pearson method at each post-baseline timepoint: Days 14, 28, 42, 56, 208, 236, Early Termination. The number and percentage of participants with seropositivity at a participant level (defined as a detectable level above LLOQ) will be provided with 2-sided 95% CI using the Clopper-Pearson method at each post-baseline timepoint.
	
Supportive: Similar tabulations will be done for the following analysis subgroups: age group, gender and country. For the priming vaccination period: the common difference of seropositivity and seroconversion rates and 95% CIs between each vaccine dose group and the placebo will be estimated using the Miettinen-Nurminen method with age group as stratification factor for each time point.

